3.7.3.7. Chemotherapy Delivery

Chemotherapy delivery will be assessed over the 24 weeks period from start of chemotherapy by dose intensity, dose reduction and treatment delays. Relative dose intensity (RDI) will be calculated based on the ratio of delivered dose intensity of chemotherapy to standard dose for the time period.

Secondary endpoints of this study are the mean RDI of chemotherapy, the proportion of participants with dose reduction $\geq 10\%$ from previous dose and the proportion of participants with treatment delays of more than 14 days in the two treatment arms at 12 weeks and 24 weeks; they will be compared between treatment arms.

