2.3. Treatment Allocation

2.3.1. Method of Treatment Allocation

Participants were randomly assigned via a computerised system using the method of minimisation (with a 80:20 random element) to receive integrated geriatric care or standard oncology care in a 1:1 ratio.(1) In this study, minimisation was used to achieve balance between groups using the following characteristics:

- treatment intent
- tumour type
- age
- gender
- ECOG performance status (physician-rated)

An 80:20 random element was determined to be the optimal value to reduce predictability whilst retaining balance.(2) This method was conducted using the MinimPy software package by a researcher not involved in the care of the study participants.(3)

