3.5.2. Other Secondary Endpoints

Other secondary endpoints will be summarised according to established guidelines specific to the measurement instrument. In general, categorical variables will be tabulated and key summary statistics (mean, standard deviation, median, range, etc.) will be presented for continuous measurements. Comparisons between treatment arms will be made where appropriate and the test selected depending on the distribution.

Secondary endpoints were specified in the protocol as follows:

- Performance Status The mean self-rated ECOG score and KPS score of patients at 12 weeks and 24 weeks are secondary endpoints; they will be compared between treatment arms.
- Functional Status The proportion of participants in each treatment arm with functional decline in the ADL and/or IADL scores at 12 weeks and 24 weeks are secondary endpoints of this study; they will be compared between treatment arms.
- Mood The proportion of participants in each of the PHQ-9 and GAD-7 categories (cut-points 5, 10 and 15) in the two treatment arms at 12 weeks and 24 weeks are secondary endpoints of this study; they will be compared between treatment arms.
- Nutrition The proportion of participants with self-MNA score ≤ 11 points and >11 points in the two treatment arms at 12 weeks and 24 weeks is a secondary endpoint of this study and will be compared between treatment arms.
- Health Utility The EQ-5D-5L health utility score in the two treatment arms at 12 weeks and 24 weeks are secondary endpoints of this study and will be compared between treatment arms.
- Chemotherapy delivery Secondary endpoints of this study are the mean RDI of chemotherapy, the proportion of participants with dose reduction $\geq 10\%$ from previous dose; they will be compared between treatment arms.
- Healthcare utilisation Secondary endpoints of this study are the mean number of: emergency department visits, hospital admissions (including length of hospital stay; and divided into planned and unplanned), medical consultations and type of PBS-listed medications in the two treatment arms from randomisation to 12 weeks and 24 weeks post-randomisation; they will be compared between treatment arms. An additional secondary endpoint is the hazard ratio for hospitalisation of participants in the two treatment arms; this will be compared between treatment arms.

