- Institutionalisation A secondary endpoint of this study is the hazard ratio of institutionalisation of participants in the two treatment arms; this will be compared between treatment arms. In addition, the level of care level of care and social situation will also be described in the treatment arms.

The following endpoint definition was changed from the protocol:

- Chemotherapy delivery: the proportion of participants with dose delays in the two treatment arms at 12 weeks and 24 weeks. Dose delay is defined as a delay of more than 3 days in the start of chemotherapy measured since the start of the previous cycle.

The following endpoints were not defined in the protocol, but will be analysed as exploratory endpoints to supplement the pre-specified secondary endpoints:

- QLU-C10D health utility
- QLU-C10D health utility score in the two treatment arms at 12 weeks and 24 weeks will be compared between treatment arms.(27, 28)
- The QLU-C10D health utility scores will also be used in the health economic analysis, in place of the EQ-5D-5L scores, to determine if the same or different conclusions would be reached with either utility measure.
- Chemotherapy delivery
- Primary dose reduction (PDR) will be compared within treatment arms. PDR is defined as dose of chemotherapy which is less than the dose recommended for given regimen in current treatment guidelines by NCCN (excluding round-off).
- Mean % dose reduction at outset will be compared within treatment arms.
- Median % dose reduction at outset will be compared within treatment arms.
- Early discontinuation of chemotherapy will be compared within treatment arms.
- Mean cycles of chemotherapy delivered will be compared within treatment arms.
- Median cycles of chemotherapy delivered will be compared within treatment arms.

Table 4. Summary of secondary and additional exploratory endpoints, data type, data timepoints and statistical tests are listed in the table below.

Endpoints	Data Type	Data output	Data Timepoints	Statistical Tests
Function				
ECOG-PS	Categorical ordinal (0,1,2,3,4)	contingency table	Baseline Wk12 Wk24	contingency table analysis
KPS	Categorical ordinal (30,40,50,60,70,80,90,100)	contingency table	Baseline Wk12 Wk24	contingency table analysis
Katz ADL scale	6-item, categorical dichotomous scale (i) → dichotomous outcome (unimpaired, impaired) (ii) → dichotomous outcome (any decrease in ADL)	1. unimpaired vs impaired 2. decrease in ADL	Baseline Wk12 Wk24	contingency table analysis

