OARS IADL	7-item, 3-point Likert scale (i) → categorical dichotomous (unimpaired, impaired) (ii) → categorical dichotomous (any decrease in IADL)	1. unimpaired vs impaired 2. decrease in IADL	Baseline Wk12 Wk24	contingency table analysis
Mood				
PHQ9 (depression)	9-item, 4-point Likert scale → categorical ordinal (none, mild, moderate, severe) → categorical dichotomous (not depressed, depressed)	contingency table	Baseline Wk12 Wk24	contingency table analysis
GAD7 (anxiety)	9-item, 4-point Likert scale → categorical ordinal (none, mild, moderate, severe) → categorical dichotomous (not anxious, anxious)	contingency table	Baseline Wk12 Wk24	contingency table analysis
Nutrition				
Self-MNA	6-item questionnaire → categorical dichotomous (malnourished/at risk vs normal) → categorical ordinal (malnourished, at-risk, normal)	1. malnourished/at risk vs normal 2. malnourished vs at-risk vs normal 3. decrease in self-MNA	Baseline Wk12 Wk24	contingency table analysis
Health Utilities				
EQ-5D-5L	5-item, 5-point Likert scale, weighted with Australian utility weights	mean utility weight	Baseline Wk12 Wk18 Wk24	t-test (parametric); or Mann-Whitney test (non-parametric)
QLU-C10D	10-dimensions derived from 13 items of the QLQ-C30, each dimension weighted with Australian utility weights	mean utility weight	Baseline Wk12 Wk18 Wk24	t-test (parametric); or Mann-Whitney test (non-parametric)
Chemotherapy Delivery				
Initial dose (i.e. primary dose reduction)	Categorical dichotomous (full dose, reduced dose)	full dose vs reduced dose	Baseline	contingency table analysis
Mean % dose reduction at outset where applicable	Numerical	mean	Baseline	t-test (parametric); or Mann-Whitney test (non-parametric)
Median % dose reduction at outset where applicable	Numerical	median	Baseline	Mann-Whitney test (non-parametric)
Subsequent dose reduction ≥10%	Categorical dichotomous (yes, no)	yes vs no		contingency table analysis
Subsequent dose escalation	Categorical dichotomous (yes, no)	yes vs no		contingency table analysis
Dose delay >3 days	Categorical dichotomous (yes, no)	yes vs no		contingency table analysis

Early discontinuation	Categorical dichotomous (yes, no)	yes vs no		contingency table analysis
Mean Relative Dose Intensity (RDI)	Numerical	mean		t-test (parametric); or Mann-Whitney test (non-parametric)
Mean cycles delivered	Numerical	mean		t-test (parametric); or Mann-Whitney test (non-parametric)
Median cycles delivered	Numerical	Median		Mann-Whitney test (non-parametric)

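### The SAP moves the treatment-delay cut-off from more than 14 days to more than 3 days with no visible reason, and plans no 14-day analysis

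*Combined protocol and SAP*

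**What the plan says.** Protocol 3.7.3.7 (Chemotherapy Delivery) lists among the secondary endpoints "the proportion of participants with treatment delays of more than 14 days in the two treatment arms at 12 weeks and 24 weeks".

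SAP 3.5.2 (Other Secondary Endpoints) has three parts that matter here:

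- **Protocol endpoints.** A list introduced by "Secondary endpoints were specified in the protocol as follows". Under chemotherapy delivery it carries relative dose intensity and dose reduction of at least 10%. It has no delay endpoint.
- **The change.** A separate item headed "The following endpoint definition was changed from the protocol". It keeps the 12- and 24-week time points and sets the new rule: "Dose delay is defined as a delay of more than 3 days in the start of chemotherapy". Counting runs from when the preceding cycle began. The 14-day figure does not appear, and no reason follows.
- **Exploratory additions.** A further list of endpoints that the protocol did not define. The delay endpoint is not among them, so it appears to keep secondary status.

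Table 4 of the SAP has one delay row, "Dose delay >3 days", and no 14-day row.

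On timing, SAP 2.3.1 reports allocation as done ("Participants were randomly assigned via a computerised system using the method of minimisation"), SAP 2.2 reports recruitment in the past tense, and the reference list includes a 2018 paper. The current protocol is version 2.0, dated 22 June 2015. SAP 2.1 describes an open-label design. SAP 3.1 says that the plan is finalised before analysis begins and is approved by the Trial Management Committee. SAP 3.4.6 applies no multiplicity adjustment to secondary endpoints.

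**The concern.** The two cut-offs answer different questions. More than 3 days captures short slippage between cycles; more than 14 days captures long interruption. A between-arm difference in one need not appear in the other, so a 3-day result cannot stand in for the protocol endpoint. Under the SAP as it stands, the protocol endpoint would not be reported at all.

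The timing adds to this. A cut-off changed late in an open-label trial, without a stated reason, invites the question of whether it was chosen with knowledge of the delivery data. SAP 2.5.1 has chemotherapy treatment recorded at weeks 12 and 24, so such data had probably accrued. A reader who has only the SAP cannot see how large the change was, because the 14-day figure is not given there.

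**Working it through.** **1. The texts side by side**

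| | Protocol 3.7.3.7 | SAP 3.5.2 and Table 4 |
|---|---|---|
| Cut-off | more than 14 days | more than 3 days |
| Time points | 12 and 24 weeks | 12 and 24 weeks (3.5.2) |
| Status | secondary | secondary by position; outside the exploratory list |
| Reason for change | not applicable | none in the visible text |
| 14-day analysis kept | not applicable | no |

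The protocol's summary of changes contains no change to this endpoint. It ends at version 2.0, so this shows only that the change came with the SAP and not by a protocol amendment listed there.

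**2. The plan's own figure**

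The documents give no expected rate, power or sample size for the delay endpoint. The only sample-size figure is for the primary endpoint: effect size 0.5, two-sided 5%, 80% power. The normal approximation gives 2 × (1.960 + 0.842)² / 0.5² = 62.8, so 63 per arm. The exact t-test gives 63.77, so 64 per arm and 128 in total, with power 0.801. The stated figure reproduces, does not depend on the delay cut-off, and is used below only as the arm size.

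**3. How far the event proportion could move (illustration)**

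If delay is measured in the same way under both rules, every delay of more than 14 days is also one of more than 3 days. The event proportion can then only stay the same or rise. To show scale, assume independent cycles with a constant chance of delay, so that P(at least one event) = 1 − (1 − p)^k:

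- 6 cycles, p = 10% (more than 3 days): 1 − 0.90⁶ = 46.9%.
- 6 cycles, p = 2% (more than 14 days): 1 − 0.98⁶ = 11.4%.
- 4 to 8 cycles, p = 10-20%: from 1 − 0.90⁴ = 34% to 1 − 0.80⁸ = 83%.
- 4 to 8 cycles, p = 2-3%: from 1 − 0.98⁴ = 8% to 1 − 0.97⁸ = 22%.

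All of these rates and cycle counts are assumptions.

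**4. False-positive risk if the cut-off were picked from the data (illustration)**

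For two independent 5% tests, the chance of at least one false positive is 1 − 0.95² = 9.75%. The two cut-offs are nested and therefore correlated, so this was simulated: no true difference, 64 per arm, two-sided pooled z-test at 5%, 200,000 trials per scenario. The assumed proportions were 10, 20 or 30% with a delay over 14 days and 40, 50 or 60% with a delay over 3 days. Selected results:

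| >14 days | >3 days | 14-day test alone | 3-day test alone | either |
|---|---|---|---|---|
| 10% | 40% | 5.1% | 5.4% | 9.7% |
| 20% | 50% | 4.8% | 4.5% | 8.5% |
| 30% | 40% | 5.2% | 5.3% | 8.2% |

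Over all nine scenarios, a single cut-off has an error of 4.4-5.4%, and either-of-two has 8.2-9.9%.

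**The case against.** The strongest reply is that the SAP is open about the change. It puts the endpoint under its own heading, directly after the list of protocol endpoints and before the exploratory ones. A reader might take the absence of delay from the protocol list as concealment. The layout does not support that: an altered endpoint has been moved out of the unaltered list and flagged. What remains is that the 14-day figure is not restated.

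A reader might also infer that the endpoint was switched because of what the data showed, and that the result is therefore biased. The documents do not support this. The SAP is to be finalised before analysis and approved by the committee. Open-label means that participants and clinicians know the arm; it does not mean that the SAP's authors saw delay counts by arm.

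Nor does the 8-10% error describe the plan as written. The SAP plans one cut-off, and one cut-off fixed blind has an error near 5%.

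The timing is itself an inference. The SAP's date is not visible in the text reviewed, because the pages before its section 1.1 were not available, and a reason could in principle stand there. The tenses are also mixed: SAP 2.4 describes the intervention in the future tense. The past-tense recruitment and allocation, together with the 2018 reference, still point to a late document.

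Finally, little rests on this endpoint. It is one of many unadjusted rows in Table 4. These replies limit the point, but none of them supplies a reason for the change or brings back the protocol analysis.

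**Conclusion.** The point holds as a gap in justification and reporting. A protocol-defined secondary endpoint has been replaced, openly but with no visible reason, in a SAP apparently written after recruitment and allocation, and its 14-day analysis is no longer planned. The documents establish a risk of data-driven choice and do not show that it occurred.

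The size is modest. One unadjusted secondary endpoint is affected; the primary endpoint, the sample size and the overall survival hierarchy are not. The event-rate contrast (47% v 11%, with ranges 34-83% v 8-22%) rests wholly on assumed inputs. The 8-10% false-positive risk is conditional on the cut-off having been picked after seeing the data, and it too uses assumed rates. The conclusion does not depend on these figures, because it follows from comparing the two sections. It concerns the analysis cut-off only and takes no position on which length of delay is clinically right.

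**What to change.** - In SAP 3.5.2 and Table 4, restore treatment delay of more than 14 days at 12 and 24 weeks as the protocol-defined secondary endpoint.
- Report the more-than-3-day result beside it, labelled as a definition introduced after the protocol.
- Under the heading that declares the change, state the protocol's 14-day figure, the reason for the change and its date, and whether delay data by arm were available to those who made it.

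**Cost.** One extra table row and a few sentences. The delay records needed for the 3-day result should also give the 14-day result, so no new data collection is expected. The downside is one more unadjusted secondary comparison; the labelling keeps clear which of the two the protocol specified.
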